5.4. Examination of Strata

The list of strata may be used in descriptive summaries and statistical analyses. Additional covariates and other strata of clinical interest may also be considered.

Category	Details
Strata	
 • Part A: stratification by geographic ancestry (Caucasian vs Japanese). • Used for ethnosensitivity comparisons. • A subset of Part A data displays will be presented with the following groups, in this order: 
 ○ Placebo (Caucasian) ○ Placebo (Japanese) ○ 450 mg GSK2831781 (Caucasian) ○ 450 mg GSK2831781 (Japanese)

5.5. Other Considerations for Data Analyses and Data Handling Conventions

Other considerations for data analyses and data handling conventions are outlined in the appendices:

Section	Component
15.3	Appendix 3: Assessment Windows
15.4	Appendix 4: Study Phases and Treatment Emergent Adverse Events
15.5	Appendix 5: Data Display Standards & Handling Conventions
15.6	Appendix 6: Derived and Transformed Data
15.7	Appendix 7: Reporting Standards for Missing Data
15.8	Appendix 8: Values of Potential Clinical Importance

6. STUDY POPULATION ANALYSES

The study population analyses will be based on the Safety population, unless otherwise specified.

Study population analyses including analyses of participant's disposition, protocol deviations, demographic and baseline characteristics, prior and concomitant medications, and exposure and treatment compliance will be based on GSK Core Data Standards.

Details of the planned displays are presented in [Appendix 12: List of Data Displays](#).

7. EFFICACY ANALYSES

There are no efficacy analyses to be included in this study.

8. SAFETY ANALYSES

The safety analyses will be based on the Safety population, unless otherwise specified.

8.1. Adverse Events Analyses

The definition of an AE is detailed in Appendix 3 of the protocol.

Analyses of AEs will include those events that are Treatment Emergent as defined in Section 15.4.

Adverse events analyses including the analysis of adverse events (AEs), Serious (SAEs) and other significant AEs will be based on GSK Core Data Standards. The details of the planned displays are provided in [Appendix 12: List of Data Displays](#).

8.2. Clinical Laboratory Analyses

Laboratory evaluations including the analyses of Chemistry laboratory tests, Haematology laboratory tests, Urinalysis, and Liver function tests will be based on GSK Core Data Standards.

Clinical laboratory summaries will include all assessments post-baseline. All clinical laboratory assessments, including pre-baseline (i.e. screening), will be listed.

The details of the planned displays are in [Appendix 12: List of Data Displays](#).

The laboratory assessments for each category are displayed below (Table 1 in Section 11.2 of the protocol):

Laboratory Assessments	Parameters			
Haematology	Platelet Count	RBC Indices: Mean Corpuscular Volume (MCV) Mean Corpuscular Haemoglobin (MCH) %Reticulocytes		White Blood Cell (WBC) count with Differential: Neutrophils Lymphocytes Monocytes Eosinophils Basophils
	Red Blood Cell (RBC) Count			
	Haemoglobin			
	Haematocrit			
Clinical Chemistry ¹	Blood Urea Nitrogen (BUN)	Potassium	Aspartate Aminotransferase (AST)/Serum Glutamic-Oxaloacetic Transaminase (SGOT)	Total and direct bilirubin
	Creatinine Estimated Glomerular Filtration Rate (eGFR)	Sodium	Alanine Aminotransferase (ALT)/Serum Glutamic-Pyruvic Transaminase	Total Protein

Laboratory Assessments	Parameters			
			(SGPT)	
	Glucose [non-fasting]	Calcium	Alkaline phosphatase	
Routine Urinalysis	
 • Specific gravity • pH, glucose, protein, blood, ketones, bilirubin, urobilinogen, nitrite, leukocyte esterase by dipstick • Microscopic examination (if blood or protein is abnormal) 			
Other Screening Tests (not to be reported)	
 • Breath alcohol screen • Urine drug screen (to include at minimum: amphetamines, barbiturates, cocaine, opiates, cannabinoids and benzodiazepines) • Serology: HIV antibody, HbsAg, HbcAb, HCV antibody, EBV antibody³, CMV antibody³, VZV antibody³ • Quantiferon test for TB 			

NOTES:
 
 1. Details of liver chemistry stopping criteria and required actions and follow-up assessments after liver stopping or monitoring event are given in Section 8.2.3 of the protocol. All events of ALT $\geq 3 \times$ upper limit of normal (ULN) and bilirubin $\geq 2 \times$ ULN (>35% direct bilirubin) or ALT $\geq 3 \times$ ULN and international normalized ratio (INR) >1.5, if INR measured, which may indicate severe liver injury (possible Hy's Law), must be reported as an SAE (excluding studies of hepatic impairment or cirrhosis). 2. Local urine testing will be standard for the protocol unless serum testing is required by local regulation or IRB/IEC. 3. To be repeated in event of possible viral reactivation. 				

Laboratory results that could unblind the study will not be reported to investigative sites or other blinded personnel until the study has been unblinded.

8.3. Other Safety Analyses

The analyses of non-laboratory safety test results including ECGs and vital signs will be based on GSK Core Data Standards, unless otherwise specified.

The non-laboratory safety test results include:

- ECGs
- Vital signs
- Local tolerability

The details of the planned displays are presented in [Appendix 12: List of Data Displays](#).

9. PHARMACOKINETIC ANALYSES

9.1. Endpoint / Variables

9.1.1. Drug Concentration Measures

Refer to [Appendix 5: Data Display Standards & Handling Conventions](#) (Section 15.5.3 Reporting Standards for Pharmacokinetic).

9.1.2. Derived Pharmacokinetic Parameters

Pharmacokinetic parameters will be calculated by standard non-compartmental analysis according to current working practices and using the currently supported version of WinNonlin. All calculations of non-compartmental parameters will be based on actual sampling times.

Pharmacokinetic parameters listed will be determined from the plasma concentration-time data, as data permits. Additional parameters may be included as required.

Parameter	Parameter Description
AUC(0-t)	
 Area under the concentration-time curve from time zero to the time of last quantifiable concentration (C(t)). Calculated using the linear trapezoidal rule for each incremental trapezoid and the log trapezoidal rule for each decremental trapezoid.
C _{max}	
 Maximum observed concentration. Determined directly from the concentration-time data.
t _{max}	
 Time to reach C_{max}. Determined directly from the concentration-time data.

9.2. Summary Measure

Descriptive statistics (n, arithmetic mean, standard deviation [SD], 95% CI, minimum, median and maximum) will be calculated by treatment (and geographic ancestry in Part A) for all PK concentrations over time and for the derived PK parameters. In addition, for log-transformed PK parameter variables, geometric mean, 95% CI and %CV_b will be provided.

9.3. Population of Interest

The primary pharmacokinetic analyses will be based on the Pharmacokinetic population, unless otherwise specified.

9.4. Strategy for Intercurrent (Post-Randomization) Events

A ‘While on-study’ strategy will be implemented for intercurrent events.

- Withdrawn participants may be replaced in the study. Replacement participants will be dosed with the planned treatment of the withdrawn participant.

- All available data from participants who were withdrawn from the study will be analysed and listed, and all available planned data will be included in summary tables and figures, unless otherwise specified.
- Missing and anomalous concentration data not due to intercurrent events will be handled according to SOP_314000.

9.5. Statistical Analyses / Methods

Details of the planned displays are provided in [Appendix 12: List of Data Displays](#) and will be based on GSK Data Standards and statistical principles.

Unless otherwise specified, endpoints / variables defined in Section 9.1 will be summarised using descriptive statistics, graphically presented (where appropriate) and listed.

9.5.1. Statistical Methodology Specification (Part A)

The following pharmacokinetic statistical analyses will only be performed if sufficient data is available (i.e. if participants have well defined plasma concentration-time profiles).

Ethnosensitivity (Part A)
Endpoint / Variables

 • AUC(0-t) • Cmax
Model Specification

 • Analysis of variance (ANOVA) will be performed on log-transformed data to determine the point estimate for the comparison of Japanese to Caucasian participants. • This analysis will be repeated for each of the PK parameters at the 450 mg dose level. • The 90% confidence interval for the mean difference of the log-transformed data will be calculated. The equivalent 90% confidence interval for the geometric means will be provided.
Model Checking & Diagnostics

 • Normality assumptions underlying the model used for analysis will be examined by obtaining a normal probability plot of the residuals and a plot of the residuals versus the fitted values (i.e. checking the normality assumption and constant variance assumption of the model, respectively) to gain confidence that the model assumptions are reasonable. • If there are any departures from the distributional assumptions, alternative models will be explored using appropriate transformed data.
Model Results Presentation

 • Table of: 
 ○ Geometric means and ratio of geometric means with 90% CI.

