5. STUDY DESIGN

5.1. Overall Design

This study is a double-blind, placebo-controlled, randomised, parallel group, two-part study, with single IV doses administered to healthy Japanese and Caucasian participants, or SC doses administered to healthy Caucasian participants.

In Part A, single IV doses of 450 mg GSK2831781 or placebo will be administered to Japanese or Caucasian healthy participants, with stratification by ethnicity.

In Part B, single SC doses of 150 mg or 450 mg GSK2831781, or placebo, will be administered to healthy Caucasian participants.

At least one interim analysis will be conducted during the study (see Section 10.5 for further details).

In line with routine pharmacovigilance, an internal GSK Safety Review Team (SRT) (which will include a subset of the 207823 study team) will review blinded safety data, including clinical laboratory parameters and adverse events, at appropriate intervals during the period of study conduct.

If, following a Safety Review Team (SRT) review, it is felt that the dose level in Part A has to be lowered from 450 mg (see Section 7.7) then the randomisation to the new dose level will also be 6:2 (GSK2831781:Placebo) within both the Japanese and Caucasian strata.

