5.2. Number of Participants

Part A: A sufficient number of participants will be randomised such that 8 evaluable Japanese participants (6:2 GSK2831781:Placebo) and 8 evaluable Caucasian participants (6:2 GSK2831781:Placebo) complete Part A, at the same dose level in each stratum. A total of 16 evaluable participants are needed to complete part A, however up to a maximum of 32 participants may be enrolled if a dose reduction is needed (see Section 7.7).

Part B: A sufficient number of participants will be randomised such that 20 evaluable Caucasian participants (8:8:4 450 mg : 150 mg : placebo) complete Part B. A total of 20 evaluable participants are needed to complete Part B, however up to a maximum of 30 participants may be enrolled if a dose reduction is needed (see Section 7.7).

Evaluable is defined as a participant who has been dosed and has safety and PK data up to Day 29.

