10.4.2. Pharmacokinetic Analyses

| Endpoint | Statistical Analysis Methods |
|-----------|---|
| Secondary | 
The PK analyses will be based on the "Pharmacokinetic" population. Plasma GSK2831781 concentration-time data will be analysed by non-compartmental methods. Calculations will be based on the actual sampling times recorded during the study. From the plasma concentration-time data, the following PK parameters will be determined, as data permit: C_{max}, t_{max}, AUC(0-t).
 
Descriptive statistics (n, arithmetic mean, standard deviation, 95% CI, minimum, median and maximum,) will be calculated for all pharmacokinetic parameters. In addition, for log e-transformed variables geometric mean, 95% confidence interval
 |

| Endpoint | Statistical Analysis Methods |
|----------|---|
| | 
and %CVb will be provided.
 
Ethnicity comparison (Part A): Analysis of variance (ANOVA) will be performed to determine the point estimate for the comparison of Japanese to Caucasian participants for each of the PK parameters AUC(0-t) and Cmax at each dose level studied, with the 90% confidence interval based on the geometric least square mean of Japanese:Caucasian participants.
 
Bioavailability Analyses (Part B): Comparative plots will be provided showing individual values by treatment for each of the PK parameters AUC(0-t) and Cmax. Plots will also be provided showing the adjusted geometric mean ratio of test to reference treatment for AUC(0-t) and Cmax together with 90% confidence intervals.
 
ANOVA will be performed as appropriate to determine the point estimate for absolute bioavailability, Fabs, with 90% confidence interval based on the geometric least square mean of test/reference ratio. The primary statistical analysis will be analysis of variance of loge-transformed AUC(0-t). Fabs is defined as follows:
 $F_{abs} = \frac{AUC(0-t)_{subcutaneous}}{AUC(0-t)_{intravenous}}$ |

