2. SUMMARY OF KEY PROTOCOL INFORMATION

2.1. Changes to the Protocol Defined Statistical Analysis Plan

Changes from the originally planned statistical analysis specified in the protocol are outlined in [Table 1](#).

Table 1 Changes to Protocol Defined Analysis Plan

Protocol	Reporting & Analysis Plan	
Statistical Analysis Plan	Statistical Analysis Plan	Rationale for Changes

 Section 7.3 of the Protocol: a single Treatment Group B is defined for the active 150 mg SC dose. 	
 Section 2.3 and Section 5.2 of the RAP: the active 150 mg SC dose in Part B corresponds to 3 treatment groups, coded B1, B2 and B3. 	
 As described in the RCCS document, the randomised allocation of active dose to syringe 1, 2 or 3 is performed as part of the main randomisation effort.

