2.3. Study Design

[figure not shown]
This study is a double-blind, placebo-controlled, randomised, parallel group, two-part study, with single IV doses administered to healthy Japanese and Caucasian participants, or SC doses administered to healthy Caucasian participants.

In Part A, single IV doses of 450 mg GSK2831781 or placebo will be administered to Japanese or Caucasian healthy participants, with stratification by ethnicity.

In Part B, single SC doses of 150 mg or 450 mg GSK2831781, or placebo, will be administered to healthy Caucasian participants.

At least one interim analysis will be conducted during the study (see Section 3.1 for further details).

In line with routine pharmacovigilance, an internal GSK Safety Review Team (SRT) (which will include a subset of the 207823 study team) will review blinded safety data, including clinical laboratory parameters and adverse events, at appropriate intervals during the period of study conduct.

Part A: Overview of Study Design and Key Features							
Part A Design Features	
 Part A will be a single centre, parallel group, single dose part. It is designed to investigate whether there are any differences due to ethnicity in safety and tolerability, or PK and PK/PD relationship in blood between healthy Japanese and Caucasian participants following a single IV 450 mg dose of GSK2831781. Separate cohorts of participants will be enrolled into Parts A and B. Part A will consist of a single cohort of 16 healthy participants, stratified by ethnicity: 8 participants will be Japanese and 8 will be Caucasian. Up to a maximum of 32 participants may be enrolled if a dose reduction is needed. The participants in each ethnicity stratum will be randomised in a 3:1 ratio to receive either 450 mg GSK2831781 IV or placebo. If a dose reduction is needed, the new participants in each ethnicity stratum will also be randomised in a 3:1 ratio to receive either GSK2831781 IV or placebo. Part A study duration, including screening and follow-up, is not expected to exceed 147 days for any participant. 						

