3. PLANNED ANALYSES

3.1. Interim Analyses

An interim analysis for Part A will be performed once at least 8 participants in each stratum have completed their Day 8 visit, and at least 6 participants in each stratum have completed their Day 29 visit, where Safety, PK and PD data will be reviewed. The interim analysis will be utilised to determine if Japanese participants can be recruited into the Phase 2 study (204869) under the existing dosing strategy.

An Interim Data Review Committee (DRC) will be utilised in this study to review the interim analysis data. The DRC will be composed of a limited number of people, who may be members of the 207823 study team, including the statistician, a senior safety representative, lead physician and the pharmacokineticist. A DRC Charter will contain the details regarding the DRC, including membership, decision rules for the interim, and required data integrity and data quality control.

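### If Part A moves to a lower dose, the SAP's ancestry ANOVA stays at 450 mg and the interim count has no same-dose condition

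*SAP*

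**What the plan says.** **Ancestry comparison.** Protocol 10.4.2 plans the Japanese-to-Caucasian ANOVA "for each of the PK parameters AUC(0-t) and Cmax at each dose level studied". SAP 9.5.1 says of the same analysis: "This analysis will be repeated for each of the PK parameters at the 450 mg dose level". SAP 2.1 introduces Table 1 with the words "Changes from the originally planned statistical analysis specified in the protocol are outlined in" that table. Its single entry concerns splitting the 150 mg SC arm into three codes.

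**Dose reduction.** Protocol 5.1 says that if the Part A dose is lowered, "then the randomisation to the new dose level will also be 6:2 (GSK2831781:Placebo) within both the Japanese and Caucasian strata". SAP 2.3 repeats the provision: "Up to a maximum of 32 participants may be enrolled if a dose reduction is needed". SAP 5.2 and 5.4 nevertheless list only 450 mg IV and placebo IV groups for Part A.

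**Counting.** Protocol 5.2 defines Part A by 8 evaluable participants per stratum who "complete Part A, at the same dose level in each stratum". The interim rule in SAP 3.1 reads: "An interim analysis for Part A will be performed once at least 8 participants in each stratum have completed their Day 8 visit". It adds a second condition of at least 6 per stratum at Day 29. Protocol 10.5 has the same two counts. Neither place mentions dose level. The interim informs whether Japanese participants may enter study 204869.

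**Outputs.** In SAP Appendix 12 the ancestry model table (Table 3.4) is a final deliverable only. Interim PK, LAG3+ and sLAG3 displays are by treatment and ancestry. The interim AE summaries (Tables 2.1, 2.2, 2.6 and 2.7) are by ancestry alone.

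**The concern.** The SAP provides for a reduced-dose cohort but gives no ancestry ratio for it. Under the protocol, such a cohort would be randomised 6:2 in each stratum and would be the one that completes Part A. Under SAP 9.5.1 as written, the ANOVA would use the 450 mg participants dosed before the change, who may be few and unevenly spread over the strata. At stake is the one prespecified ratio with a confidence interval that addresses Part A's main question.

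The interim raises a separate issue. Participants dosed at 450 mg before a reduction could count towards the 8 and the 6, together with participants at the new dose. The review could then take place before either dose level has its planned number.

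**Working it through.** **Inputs**
- Between-subject CV at 5 mg/kg, which the protocol takes as a good approximation for 450 mg: 24.2% for AUC(0-t) and 22.2% for Cmax (protocol 10.2.1).
- Planned active participants per stratum: 6. Confidence level: 90%.
- Number on active drug at 450 mg before any reduction: not given, so a range is assumed.

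**Step 1: reproduce the plan's own precision figure.**

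Log-scale SD = sqrt(ln(1 + CV²)). This is 0.2386 for AUC and 0.2193 for Cmax.

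Upper 90% bound for one geometric mean with n = 6: exp(t(0.95, 5) × SD / sqrt(6)) − 1.
- AUC: +21.7%
- Cmax: +19.8%

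Both match protocol 10.2.1. The corresponding lower bounds are −17.8% and −16.5%.

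**Step 2: precision of the Japanese:Caucasian ratio.**

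Multiplier = exp(t(0.95, nJ + nC − 2) × SD × sqrt(1/nJ + 1/nC)). The interval runs from the estimate divided by the multiplier to the estimate times the multiplier.

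| Active participants, one stratum v the other | AUC multiplier | Cmax multiplier |
|---|---|---|
| 6 v 6 (a completed cohort) | 1.28 | 1.26 |
| 4 v 4 (assumed) | 1.39 | 1.35 |
| 3 v 3 (assumed) | 1.51 | 1.46 |
| 2 v 2 (assumed) | 2.01 | 1.90 |
| 5 v 1 (assumed) | 1.75 | 1.67 |
| 3 v 1 (assumed) | 2.24 | 2.09 |
| 3 v 0 | no ratio | no ratio |

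For AUC at 3 v 3: exp(t(0.95, 4) × 0.2386 × sqrt(2/3)) = 1.51. The last row is possible because the staggered start allows 3 participants in one stratum to be dosed before dosing opens up (SAP 2.3).

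**Step 3: the interim counts.** Suppose each stratum has 3 participants (active or placebo) at 450 mg and then 5 at a new dose.
- Day 8: 3 + 5 = 8, so the first condition is met with 5 of the 8 planned at the new dose.
- Day 29: 3 + 3 = 6, so the second is met once 3 of those 5 reach Day 29.

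If the new dose is allocated 6:2 within a block of eight (block size is an assumption), 3 participants could include both placebos and so only 1 active.

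**The case against.** The case against has several parts.

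- **The Part A text does not say only.** SAP 9.5.2 restricts the bioavailability ANOVA to 450 mg and nothing else; SAP 9.5.1 does not use that word. Since 450 mg is the sole planned Part A dose, the two documents describe the same analysis unless the dose is lowered. This stands as a reading of intent: the SAP probably names the planned dose and overlooks the contingency. It still leaves no rule for the contingency.
- **Ancestry is examined elsewhere.** SAP 10 and 12 investigate inter-ethnic differences through PopPK and PK/PD models with no 450 mg limit, and SAP 9.2 gives geometric means with 95% CIs by treatment and ancestry. This stands. What is missing is the ANOVA ratio and its interval, in an estimation study with no formal hypotheses.
- **An amendment would intervene.** Protocol 8.2.1 and 8.3 require a substantial amendment before restarting after an SAE stop or a safety halt, and the SAP could be revised then. This stands in part. Protocol 7.7 also allows a reduction after review by the Safety Review Team for events short of the stopping criteria, and a revision at that point would follow the first data.
- **The trigger is silent rather than permissive.** Decision rules are in the Data Review Committee charter, which is not available here. The question in SAP 3.1 concerns the existing dosing strategy, and protocol 10.5 permits a further interim after Day 112. These are fair limits on the interim point.

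A reader might infer that the decision on Japanese entry would rest on the 450 mg ANOVA or on pooled-dose PK. The documents do not support that: the ANOVA table is not an interim output, and interim PK and PD displays are split by treatment. The interim outputs that would mix doses as specified are the AE summaries by ancestry.

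**Conclusion.** The point holds and should be corrected, with its reach limited to a Part A dose reduction. In that event the SAP's stated rule gives the ancestry ratio for the truncated 450 mg cohort and omits the completed one. The 90% CI multiplier for AUC is 1.28 for the omitted 6 v 6 comparison. It is 1.51 to 2.01 if the 450 mg cohort stopped at 3 v 3 or 2 v 2, and there is no ratio if one stratum has no active participants. The cohort sizes are assumptions; the CV is the protocol's.

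The interim weakness is separate and smaller. With no same-dose condition, the review could be triggered with fewer than the planned participants at any one dose. That it would count participants at different doses is inferred from silence, and the committee charter may already deal with it.

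It would go too far to say that the reduced-dose cohort gets no ancestry analysis, because the population models and descriptive summaries remain.

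**What to change.** 1. **SAP 9.5.1:** replace the reference to 450 mg with the protocol's scope, every dose level studied. Otherwise, record and justify the narrowing in SAP Table 1.
2. **SAP 3.1 and protocol 10.5:** require both counts, 8 per stratum at Day 8 and 6 per stratum at Day 29, at the same dose level.
3. **SAP Appendix 12:** if the dose is lowered, present interim AE tables by dose level as well as ancestry.

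No dose is proposed, and no ranking of one dose level's result above another is needed. The cost is a few wording changes, one of them in the protocol, and a later interim if the dose is reduced. If it is never reduced, the analysis and its timing are unchanged.
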